16.5. Appendix 5 – Safety Reporting Flow Chart

Activity	Responsibility	Timing	Comments
Review medical	Trial staff	Days 3, 5, 8, 11, 15, 29	Recorded on eCRF system. Where Trial
records for evidence			Staff are not available on these specific
of AEs whilst in			days this should be completed asap.
hospital or ask			
participant if			
discharged.			
Review of recorded	PI (or	Within 24 hour of	Recorded on eCRF and/or medical
AEs for causality	delegate)	recording	records.
and seriousness			
Reporting SAEs - All	PI (or	Within 24 hours of	SAE form:
SAEs need to be	delegate)	becoming aware of SAE	https://www.ahspartnership.org.uk/tasc/for-
assessed and			researchers/sops/safety-and-
signed off by the PI			pharmacovigilance
or delegated doctor.			Reported to:
			[contact]
			[contact]
Reviewing of SAEs	Sponsor	Within 24 hours of	
		receiving SAE form	
Reporting of	Sponsor	Within 7 days if life	
SUSARs to MHRA		threating or fatal.	
		Within 15 days for others	

16.6. Appendix 6 – Amendment History

Amendment	Protocol	Date	Author(s)	Details of changes made
No.	version no.	issued	of changes	
N/A prior to	2	04-05-20	[name]	Requested by MHRA:
full approval			[name]	Inclusion criteria to include hospitalised participants.
				Contraception to be used for 30 days after last dose of IMP.
AM02	3	20-05-20	[name]	Removal of the requirement for Caldicott Guardian approval for research staff to identify potential participants. Conforms to advice from Confidentiality Advisory Group and Public Benefit and Privacy Panel.
				Additional guidance on handling Informed Consent Form with COVID-19 patients.
				Minor clarifications to protocol.
AM04	4	30-06-20	[name]	Inclusion criteria to include clinically suspected COVID-19.
				Exclusion criteria to exclude currently taking phenytoin or rifampicin
				Clarification of co-enrolment.
				Clarification of handling ICF
				Addition of visit instead of phone call for participants at day 29 (Tayside only).
				Itraconazole, Ketoconazole, diltiazem, verapamil, phenytoin or rifampicin added as trial restrictions
				Minor clarifications to protocol.
AM07	5	03-07-20	[name]	Update of consent process to reflect process requested by and confirmed with REC for AM05 approval
				Addition of Sheffield to take research bloods
				Clarification that day 1 of trial will be day of first dose of IMP
AM09	6	19-08-20	[name]	Update eligibility with criteria for hospitalisation timelines
				Update eligibility with excluded medications
				Update on trial restrictions – excluded medications

				Removal of long-term follow-up
				Clarification on IMP accountability procedures for discharged participants,
				Clarification on safety reporting flow chart
				Addition of recording SARS CoV-2 PCR results when done for clinical reasons
AM12	7	10-10-20	[name]	3.7 Exploratory blood analysis omitted if no lab capacity
				16.4 Clarification that research samples taken on Day 29 for Tayside & Sheffield
AM13	8	12-12-20	[name]	I Addition of Key Contacts
			[name]	Update to background with current scientific knowledge
				6.2 Exclusion criteria changed to: Current treatments with potent Cyp3A4 inducers/inhibitors (e.g Itraconazole, Ketoconazole, diltiazem, verapamil, phenytoin or rifampicin)
				7.1 & 10.2 Recruitment to continue beyond 300, final recruitment target will be confirmed after the evaluation of the power calculation
				9.3 & 16.5 Clarification of SAE reporting process
				10.1 Update to blinded endpoint confirmation process.
AM14	9		[name]	Update to sample size and justification of change

#### 2 Abbreviations and Definitions

AE	Adverse Event
CRF	Case Report Form
IMP	Investigational Medical Product
SAP	Statistical Analysis Plan

## 3 Introduction

## 3.1 Preface

COVID-19 is a respiratory disease caused by a novel coronavirus severe acute respiratory syndrome coronavirus-2 (SARS-CoV-2) and causes substantial morbidity and mortality. This clinical trial is designed to evaluate the potential of Brensocatib as a novel host directed therapy for the treatment of adult patients hospitalised with COVID-19. We hypothesise that Brensocatib, by blocking damaging neutrophil proteases, will reduce the incidence of acute lung injury and acute respiratory distress syndrome (ARDS) in patients with COVID-19, thereby resulting in improved clinical outcomes at day 15 and day 29, fewer days dependent on oxygen or mechanical ventilation, and shorter length of hospital stay.

## 3.2 Purpose of the analyses

These analyses will assess the efficacy and safety of Brensocatib in comparison with placebo and will be included in the clinical study report.

## 4 Study Objectives and Endpoints

## 4.1 Study Objectives

The overall objective of the study is to evaluate the clinical efficacy of Brensocatib compared to placebo on top of standard care in adult patients hospitalised with COVID-19.

## 4.2 Endpoints

## **Primary outcome**

The primary outcome is participant clinical status (on a 7-point ordinal scale) at day 29.

#### Secondary outcome

## Clinical severity:

- 1. Time to an improvement of one category from admission to day 29 using 7-point ordinal scale
- 2. Clinical status on 7-point ordinal at days 3, 5, 8, 11, 15 and 29
- 3. Change on 7-point ordinal from baseline to day 15
- 4. Proportion of participants showing improvement on 7-point ordinal scale at day 15
- 5. Mean change in the 7-point ordinal scale from baseline (day 1) to days 3, 5, 8, 11, 15 and 29.

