3.7. Table of endpoints/outcomes

Objectives	Outcome Measures	Timepoint(s)
Primary Objective Participant clinical status (on a 7- point ordinal scale) In accordance with WHO recommendations the primary endpoint will be determined by a pilot trial of the first 100 participants.	 7-point ordinal scale: Not hospitalised, no limitations on activities Not hospitalised, limitation on activities; Hospitalised, not requiring supplemental oxygen; Hospitalised, requiring supplemental oxygen; Hospitalised, on non-invasive ventilation or high flow oxygen devices; Hospitalised, on invasive mechanical ventilation or ECMO (Extracorporeal membrane oxygenation) Death. 	Up to day 29
Secondary Objectives	Outcome Measures	Timepoint(s)
Evaluate the clinical efficacy of Brensocatib relative to standard care in adult patients hospitalised with COVID-19	Clinical Severity Time to an improvement of one category from admission using 7-point ordinal scale. Participant clinical status on 7-point ordinal scale Mean change in the 7-point ordinal scale	Daily whilst hospitalised Days 3, 5, 8, 11, 15 and 29. Baseline to days 3, 5, 8, 11, 15 and 29.
	National Early Warning Score (NEWS): Time to discharge or to a NEWS of ≤ 2 and maintained for 24 hours, whichever occurs first. Change from baseline Oxygenation:	Daily whilst hospitalised Days 8, 15, 29
	Oxygen free days Incidence and duration of new oxygen use during the trial	1-29 days 0-29 days
	Mechanical Ventilation: Ventilator free days	1-29 days

	Incidence and duration of new mechanical ventilation use during the trial.	1-29 days
	Hospitalisation:	
	Duration of hospitalisation (days).	Date of admission and discharge
	Mortality:	
	28-day mortality	Date of death
Evaluate the safety of the	Cumulative incidence of SAEs	1-29 days
intervention through 28 days of follow-up as compared to the control arm	Discontinuation or temporary suspension of treatment	1-29 days
	Changes in white cell count, haemoglobin, platelets, creatinine, total bilirubin, ALT, and AST over time (hospitalised participants only)	Days 0/1, 3, 5, 8, 11, 15, 29
	Adverse events of special interest- hyperkeratosis, infections and dental complications	1-29 days
	dental complications	
Exploratory Objectives	Outcome Measures	Timepoint(s)
Exploratory Objectives Evaluate the virologic efficacy of Brensocatib	·	Timepoint(s) Day 15 and day 29

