6.1. Inclusion criteria

- Male or female
- ≥16 years of age
- SARS-CoV-2 infection (clinically suspected* or laboratory confirmed*).
- Admitted to hospital as in-patient less than 96 hours prior to randomisation^
- Illness of any duration, and at least one of the following:
 - Radiographic infiltrates by imaging (e.g. chest x-ray, computed tomography (CT) scan)
 OR
 - Evidence of rales/crackles on physical examination
 - Peripheral capillary oxygen saturation (SpO2)≤94% on room air prior to randomization
 OR
 - Requiring supplemental oxygen.
 - Lymphocyte count <1 x 10⁹ cells per litre (L)
- Participant (or legally authorized representative) provides written informed consent
- Able to take oral medication
- Participant (or legally authorised representative) understands and agrees to comply with planned trial procedures.

*Laboratory-confirmed: SARS-CoV-2 infection as determined by polymerase chain reaction (PCR), or other commercial or public health assay in any specimen < 96 hours prior to randomization.

*Clinically suspected: in general, SARS-CoV-2 infection should be suspected when a patient presents with (i) typical symptoms (e.g. influenza-like illness with fever and muscle pain, or respiratory illness with cough and shortness of breath); and (ii) compatible chest X-ray findings (consolidation or ground-glass shadowing); and (iii) alternative causes have been considered unlikely or excluded (e.g. heart failure, influenza). However, the diagnosis remains a clinical one based on the opinion of the managing doctor

^Where a patient has been admitted to hospital for a non COVID-19 reason and develops COVID-19 symptoms whilst an in-patient, randomisation may occur up to 96 hours from onset of symptoms.

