8.7. Dosage schedules

Route of administration: oral. Where a participant is unable to take oral medication they will be excluded from the trial. If during the treatment phase a participant becomes unable to take oral medication their treatment will be given by nasogastric tube (NGT) where the participant has this in place for clinical reasons. After crushing, the tablet should be placed in water for 5-10 mins, after pushing through NGT, flush with 10 mL of water (or saline), and clamp NGT for 30 mins.

Frequency of administration: once daily, before breakfast. On day of randomisation the first dose may be given up to 5pm, after that point the first dose should be given the following day before breakfast. The day of first dose received will be deemed to be day 1 of the trial.

Missed doses: if a dose is missed this should be given within 10 hours of the missed dose.

Maximum duration of treatment: 28 days. Where a participant misses a dose due to being unable to take oral medication, or for any other reason, the treatment duration will not be extended.

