#### 5.2.1 Inclusion criteria

- Male or female
- $\geq 16$  years of age
- SARS-CoV-2 infection (clinically suspected+ or laboratory confirmed\*).
- Admitted to hospital as in-patient less than 96 hours prior to randomisation^
- Illness of any duration, and at least one of the following:
  - Radiographic infiltrates by imaging (e.g. chest x-ray, computed tomography (CT) scan)

OR

- Evidence of rales/crackles on physical examination OR
- Peripheral capillary oxygen saturation (SpO2) ≤94% on room air prior to randomization

OR

Requiring supplemental oxygen.
 OR

- Lymphocyte count <1 x 109 cells per litre (L)
- Participant (or legally authorized representative) provides written informed consent
- Able to take oral medication
- Participant (or legally authorised representative) understands and agrees to comply with planned trial procedures.

\*Laboratory-confirmed: SARS-CoV-2 infection as determined by polymerase chain reaction (PCR), or other commercial or public health assay in any specimen < 96 hours prior to randomization.

+Clinically suspected: in general, SARS-CoV-2 infection should be suspected when a patient presents with (i) typical symptoms (e.g. influenza-like illness with fever and muscle pain, or respiratory illness with cough and shortness of breath); and (ii) compatible chest X-ray SAP version 2 STOP COVID-19

05-04-2021

Page 10 of 46

findings (consolidation or ground-glass shadowing); and (iii) alternative causes have been considered unlikely or excluded (e.g. heart failure, influenza). However, the diagnosis remains a clinical one based on the opinion of the managing doctor

^Where a patient has been admitted to hospital for a non COVID-19 reason and develops COVID-19 symptoms whilst an in-patient, randomisation may occur up to 96 hours from onset of symptoms.

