#### 9.2.11 Duration of hospital stay - days

Duration of hospitalization will be calculated only for participants who are discharged alive on or prior to Day 29 and will be compared between the treatment arms using negative binomial regression.

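### Time to improvement and (in the protocol) hospital stay are anchored at admission, not randomisation: the reference category is not scheduled for collection, and pre-treatment days dilute the stay comparison

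*SAP*

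**What the plan says.** SAP 4.2 defines the first clinical-severity outcome as "Time to an improvement of one category from admission to day 29 using 7-point ordinal scale". Protocol 3.7 has "Time to an improvement of one category from admission using 7-point ordinal scale".

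For duration of hospitalisation, the timepoint entry in protocol 3.7 is "Date of admission and discharge". The SAP names the outcome in 4.2 without a start date. SAP 9.2.11 adds only a restriction: "Duration of hospitalization will be calculated only for participants who are discharged alive on or prior to Day 29".

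Protocol 6.1 requires patients to be "Admitted to hospital as in-patient less than 96 hours prior to randomisation". There is one exception: "Where a patient has been admitted to hospital for a non COVID-19 reason and develops COVID-19 symptoms whilst an in-patient", the 96 hours run from symptoms instead (SAP 5.2.1: "randomisation may occur up to 96 hours from onset of symptoms"). No limit on time since admission then applies.

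Trial day 1 is the day of first dose (protocol 8.7 and the schedule footnotes in both documents). It can fall after the day of randomisation. The first dose may be given on that day up to 5pm, and "after that point the first dose should be given the following day before breakfast".

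**The concern.** The drug cannot affect days before randomisation. If they are counted, they add the same quantity to both arms, pull a ratio of stays towards 1 and add variance. If admission instead supplies the category against which improvement is judged, the trial needs a score that its schedule does not ask for. Two programmers working from the SAP could then derive different event dates for the same patient.

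The precision of two secondary comparisons is at stake. SAP 7.6 names time to improvement and duration of hospitalisation among the key secondary endpoints of the preliminary analysis.

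**Working it through.** **1. The anchors side by side**

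| Quantity | Anchored at | Where |
|---|---|---|
| Time to improvement | Admission | SAP 4.2; protocol 3.7 |
| Hospital stay | Admission (protocol); not stated (SAP) | Protocol 3.7; SAP 4.2, 9.2.11 |
| Mean change in ordinal score | Day 1 | SAP 4.2, same list |
| Day 1, hence day 29 | First dose | Protocol 8.7; schedule footnotes |
| First scheduled ordinal score | Screening, day 0 or 1 | Protocol Appendix 4; SAP 5.4 |

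The window for time to improvement thus opens on one clock and closes on another. On the protocol's definition, so does hospital stay, because the day-29 restriction in SAP 9.2.11 is counted from first dose. The Cox section (SAP 9.2.1) restates no origin and gives no delayed-entry rule.

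**2. Both readings of the improvement endpoint**

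- *Admission is time zero.* Patients count as at risk on days when no trial score was due.
- *Admission is the reference category.* That score is not scheduled, and protocol 7.8 has screening procedures recorded only after consent. The choice matters: a patient in category 3 on admission, 4 at randomisation and 3 later has improved on the randomisation score but not on the admission score.

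**3. The plan's own figure**

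Neither document gives an effect size or power for these two endpoints. The only sample size is for the primary endpoint. With the Whitehead formula and the plan's control proportions at OR 2.0, two-sided 5% and 85% power:

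N = 12(z₀.₉₇₅ + z₀.₈₅)² / [ln(OR)² (1 − Σp̄ᵢ³)] = 12 × 8.98 / (0.480 × 0.831) ≈ 270, against 272 stated.

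It reproduces, and this point does not change it.

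**4. Hospital stay, closed form (assumed inputs)**

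Let m be the control mean stay after randomisation, R the true ratio and L the mean lag from admission to randomisation. The ratio counted from admission is (mR + L)/(m + L), and the share of the effect on the ratio that is lost is L/(m + L). With R = 0.80:

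- m = 6: L = 1 gives 5.8/7 = 0.83; L = 2 gives 6.8/8 = 0.85; L = 4 gives 8.8/10 = 0.88.
- m = 10: L = 1 gives 9/11 = 0.82; L = 2 gives 10/12 = 0.83; L = 4 gives 12/14 = 0.86.

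At L = 2 the share lost is 2/8 = 25% or 2/12 = 17%. The absolute difference in days, m(1 − R), does not change.

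**5. Simulation (assumed inputs)**

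400 patients, 1:1. Stay: negative binomial with dispersion 0.5, true ratio 0.80, 300 runs. Improvement: Cox, exponential times censored at 28 days, true HR 1.35, 400 runs. The usual lag is uniform on 0 to 4 whole days. The second scenario gives 10% of patients a lag of 5 to 30 days. Each cell shows the randomisation clock, then the admission clock.

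| Endpoint | Lag | Estimate | Power |
|---|---|---|---|
| Stay, mean 6 d | 0–4 d | 0.80 → 0.85 | 82% → 77% |
| Stay, mean 10 d | 0–4 d | 0.80 → 0.83 | 82% → 80% |
| Stay, mean 6 d | with 10% long | 0.80 → 0.87 | 75% → 49% |
| Stay, mean 10 d | with 10% long | 0.80 → 0.86 | 79% → 59% |
| Improvement, median 5 d | 0–4 d | 1.36 → 1.35 | 83% → 83% |
| Improvement, median 8 d | 0–4 d | 1.35 → 1.35 | 82% → 80% |
| Improvement, median 5 d | with 10% long | 1.35 → 1.26 | 83% → 66% |
| Improvement, median 8 d | with 10% long | 1.37 → 1.31 | 86% → 74% |

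Both clocks use the same simulated patients, so the loss within a row is more reliable than either level. Power on the randomisation clock should not depend on the lag; the 75% and 82% for a mean stay of 6 days show the run-to-run noise. The stay model omits the restriction to patients discharged alive.

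With no true effect, estimates were about 1.00 on both clocks. Rejection rates were 4.3% to 6.3% for stay and 2.8% to 8.0% for improvement. The standard error at 5% with 400 runs is √(0.05 × 0.95/400) = 1.1 points. The 8.0% compares with 6.5% on the randomisation clock in the same data.

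Keeping the admission clock but entering patients at randomisation brings the two long-lag hazard ratios back to 1.34 and 1.36.

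**The case against.** The best defence is that this is loose wording. Improvement from admission can be read as naming a reference state. The only usable scores are those at screening and randomisation, and SAP Table 5 summarises status at randomisation. The protocol's admission and discharge dates may simply list what is collected, since they stand in the timepoint column. Total stay from admission is also a legitimate quantity to report. All of this is fair. It shows that the plan leaves the origin to the analyst; it does not supply one.

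The defence is also right about size. Large losses appear only with an assumed share of long-lag patients, and neither document gives that share or any lag distribution.

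A reader might infer four stronger things that the documents do not support:

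- *That both documents count stay from admission.* Only the protocol does; the SAP is silent.
- *That the dilution of the stay ratio carries over to time to improvement.* A Cox model depends on the ordering of event times, and with lags of up to 4 days the hazard ratio hardly moves.
- *That the comparison is biased towards a false positive.* The lag precedes randomisation and is balanced in expectation. The null simulations are noisy, but this argument does not rest on them.
- *That any patient may have waited longer than 96 hours.* Only the in-hospital-onset exception allows it.

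**Conclusion.** The point holds as a problem of definition and precision on two secondary endpoints. For time to improvement, the stated anchor is either a clock that starts before treatment or a category that the trial does not schedule. It also conflicts with the day-1 baseline in the same SAP list. For hospital stay, the protocol's definition brings pre-randomisation days into the comparison and the SAP does not replace it.

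With lags of 0 to 4 days and a true stay ratio of 0.80, power for stay falls by about 2 to 5 points. For time to improvement the loss is 0 to 2 points. With an assumed 10% of patients lagged 5 to 30 days, the losses are about 20 to 26 points for stay and 12 to 17 for improvement. Stay lengths, effects and lags are all assumptions. The primary day-29 endpoint and the sample size are not affected.

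**What to change.** In SAP 4.2, 9.2.1 and 9.2.11 and protocol 3.7, set one time zero for both endpoints: the date of randomisation.

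- Improvement: the first day with a score at least one category better than the ordinal score recorded at randomisation, timed from randomisation.
- Hospital stay: days from randomisation to discharge.
- State that trial day 1 is the day of first dose and may fall a day after randomisation. The two must not be treated as the same, and the end of the window should be written accordingly.
- Report stay before randomisation as a baseline characteristic and total stay from admission descriptively.

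The cost is wording. The dates and the randomisation score are already part of planned data collection. If the protocol is not amended, SAP section 14, which now reports no changes, should record the departure. The choice should be fixed before any unblinded analysis, including the preliminary one, so that it cannot appear to depend on the results.

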#### National Early Warning Score (NEWS):

- 1. Time to discharge or to a NEWS of  $\leq$  2 and maintained for 24 hours, whichever occurs first.
- 2. Change from baseline to days 3, 5, 8, 11, 15 and 29

#### Oxygenation:

- 1. Oxygen free days
- 2. Incidence and duration of new oxygen use during the trial

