## 9.2.6 No of days free from oxygen

Number of days free from oxygen support will be compared between the treatment arms using the negative binomial regression with time in ICU as the offset. Number of days will be calculated as the number of days free from oxygen support reported on the 7-point ordinal scale eCRF.

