## 9.2.7 Duration of new oxygen used

Duration of new oxygen used will be calculated and will be compared between the treatment arms using the negative binomial regression with time in ICU as the offset.

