## 9.2.8 Number of patients receiving new mechanical ventilation

The number and percentage of participants who received new mechanical ventilation will be presented. Comparison between the treatment arms will be performed using a Fisher's Exact test.

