## 14 Summary of Changes to the Protocol

There are no changes to report.

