## Oxygenation

No of days free from oxygen

Duration of new oxygen use

Mechanical ventilation

Number of patients receiving new mechanical ventilation

No of days free from ventilation

Duration of new ventilation used

Duration of hospital stay - days

28-day mortality

Table 10: Safety analyses

	Brensocatib N =	Placebo N =	Effect estimate (95% CI)
% of patients with at least 1 AE			
Incidence of SAEs			
Discontinuation or temporary suspension of treatment			
Changes in white cell count			
Changes in haemoglobin			
Changes in platelets			
Changes in creatinine			
Changes in total bilirubin			
Changes in ALT			
Changes in AST			
Adverse events, n (%):			
Hyperkeratosis (Skin)			
Infections			
Dental complications			

Table 11: Adverse Events

Adverse Event - n (%)	Brensocatib	Placebo
	N =	N =
Death		
Life-threatening		
Required hospitalisation		
Resulted in persistent or significant disability		
Medically significant		
Total		

Table 12: Summary of all adverse events - System Organ Class Level

N = N =	Total	Placebo	Brensocatib
	N=	N =	N =

Number of participants

Number of participants with adverse events

Number of participants without adverse events

Number of adverse events

Cardiac disorders

Eye disorders

Gastrointestinal disorders

General disorders and administration site conditions

Infections and infestations

Injury, poisoning and procedural complications

Investigations

Metabolism and nutrition disorders

Musculoskeletal and connective

tissue disorders

Nervous system disorders

No Code

Psychiatric disorders

Renal and urinary disorders

Respiratory, thoracic and mediastinal disorders

Skin and subcutaneous tissue

disorders

Vascular disorders

Table 13: Summary of all adverse events - Preferred Term Level

Brensocatib	Placebo	Total
N =	N =	N=

Number of participants

Number of participants with adverse

events

Number of participants without adverse

events

Number of adverse events

Abdominal discomfort

Abdominal pain

Acute kidney injury

Arthralgia

Back pain

Blood glucose increased

Bradycardia

Cerebrovascular accident

Chest discomfort

Chest pain

Clostridium difficile infection

Constipation

Cough

Delirium

Diarrhoea

Dizziness

Drug eruption

Dry mouth

Dry skin

Dysarthria

Dyspepsia

Dyspnoea

Dysuria

Electrocardiogram abnormal

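### The SAP lists incidence of new oxygen use as a secondary endpoint but gives it no analysis or table row, and the analysis of its duration names no at-risk group

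*SAP*

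**What the plan says.** Protocol 3.7 and SAP 4.2 (Oxygenation) carry the same endpoint: "Incidence and duration of new oxygen use during the trial". SAP 4.2 words the mechanical ventilation endpoint in the same two-part way.

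SAP 9.2 has two oxygen analyses:

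- Section 9.2.6 covers oxygen-free days: "Number of days will be calculated as the number of days free from oxygen support reported on the 7-point ordinal scale eCRF".
- Section 9.2.7 covers duration. It is to be "compared between the treatment arms using the negative binomial regression with time in ICU as the offset". The section does not define new oxygen and names no subset.

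For ventilation, SAP 9.2.8 adds an incidence analysis: "The number and percentage of participants who received new mechanical ventilation will be presented", with Fisher's exact test.

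Shell Table 9 follows the same pattern. Under oxygenation it has the oxygen-free-days row and "Duration of new oxygen use". Under ventilation it also has "Number of patients receiving new mechanical ventilation".

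On who is analysed, needing oxygen is one of the qualifying criteria (SAP 5.2.1), and SAP 7.3.2 expects baseline categories 3, 4 and 5. SAP 7.2.1 and Protocol 10.5 take everyone randomised and dosed. Where the SAP wants a subset for a duration it says so: hospital stay in 9.2.11 is limited to those discharged alive by day 29.

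**The concern.** A listed secondary endpoint has no specified treatment comparison. Protocol 10.2.3 defers secondary analyses to the SAP, so nothing else supplies one. If incidence is reported, its definition and denominator would have to be chosen later, possibly after results by arm are known. SAP 7.6 already plans a preliminary efficacy analysis on an unlocked database.

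The duration analysis has a related gap. Only participants at category 3 are off oxygen at baseline. For those at category 4 or 5 the SAP does not say whether they are left out, scored zero, or counted if they come off oxygen and restart. These choices give different estimates from the same data. The offset adds a further difficulty, because many participants who start oxygen on a ward may never enter ICU.

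**Working it through.** **1. Endpoint against analysis**

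| Listed in SAP 4.2 | Analysis in SAP 9.2 | Row in Table 9 |
|---|---|---|
| Oxygen-free days | 9.2.6 | yes |
| New oxygen: incidence | none | none |
| New oxygen: duration | 9.2.7 | yes |
| Ventilation-free days | 9.2.9 | yes |
| New ventilation: incidence | 9.2.8 | yes |
| New ventilation: duration | 9.2.10 | yes |

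Of the six components, only the incidence of new oxygen use has neither an analysis nor a row.

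**2. Effect of an unrestricted duration analysis**

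The documents give no figure for new oxygen use or for the share on oxygen at entry, so there is no plan figure to reproduce. The inputs below are assumptions, apart from 200 per arm (400 randomised 1:1).

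Let f be the share at risk (category 3), m the mean days of new oxygen among those at risk, and v their squared coefficient of variation. Score everyone else zero and ignore the offset.

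- Mean in all participants: f·m. With the same f in both arms, as randomisation gives on average, f cancels from the ratio of means. The ratio is unchanged.
- Variance of the log mean, at-risk only: v/(f·n).
- Variance of the log mean, everyone: ((1+v)/f − 1)/n.
- Ratio of the two: (1 + v − f)/v.

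| f | v | Calculation | Variance ratio |
|---|---|---|---|
| 0.2 | 1 | 1.8/1 | 1.80 |
| 0.3 | 2 | 2.7/2 | 1.35 |
| 0.4 | 3 | 3.6/3 | 1.20 |

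The middle row with n = 200 is 2/(0.3 × 200) = 0.033 against (3/0.3 − 1)/200 = 0.045. A variance ratio of 1.20 to 1.80 means a standard error 10% to 34% larger (√1.20 = 1.10, √1.80 = 1.34). The at-risk group would be 0.2 × 400 = 80 to 0.4 × 400 = 160 people.

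A negative binomial simulation without offset, assuming new oxygen in 40% vs 25% of those at risk, agrees in direction:

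| f | Rate ratio, at-risk / all | SE of log ratio, at-risk / all | Mean difference in days, at-risk / all | Power, at-risk / all |
|---|---|---|---|---|
| 0.3 | 0.61 / 0.61 | 0.482 / 0.549 | −1.08 / −0.32 | 13% / 10% |
| 0.5 | 0.61 / 0.61 | 0.371 / 0.409 | −1.09 / −0.55 | 23% / 15% |

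The variance ratios here are (0.549/0.482)² = 1.30 and (0.409/0.371)² = 1.22. Fits at f of 0.2 or less were unstable and are not used.

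**3. Same question for incidence**

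Assumed new oxygen use is again 40% vs 25% of those at risk, with 200 per arm, two-sided 0.05. The risk ratio is 0.25/0.40 = 0.625 whichever denominator is used.

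| f | Risk difference, at-risk / all | Power, at-risk / all |
|---|---|---|
| 0.2 | 15 / 3 points | 30% / 23% |
| 0.3 | 15 / 4.5 points | 42% / 33% |
| 0.4 | 15 / 6 points | 53% / 43% |

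**4. The offset**

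A count model conventionally takes the log of exposure time as its offset. The log of zero ICU time is undefined, so a participant who never enters ICU cannot contribute to 9.2.7 as written. Entry to ICU happens after randomisation, so the analysed group would be selected on a post-randomisation event. The figures in step 2 leave the offset out and describe the zero-scoring question alone.

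**The case against.** The best counter-argument is that the endpoint is not lost. SAP 4.2 still lists it, SAP 8 promises frequencies and percentages for categorical measures, and Protocol 10.2 says secondary hypotheses will be described by proportions where data are categorical. SAP 9.2.2 and 9.2.3 report category counts and point changes at scheduled days. This stands to the extent that a reader should not infer that the result will certainly go unreported. None of these passages gives a definition, a denominator or a comparison between arms, so the gap remains.

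Four stronger readings are tempting and not supported:

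- **The treatment effect is diluted.** The planned measure is a ratio, and balanced zeros leave it unchanged. Only precision and the absolute difference suffer.
- **Participants already on oxygen enter as zeros.** SAP 9.2.7 does not say so. They could equally be excluded or counted on restarting.
- **The endpoint was dropped without declaration.** SAP 14 says "There are no changes to report". As the endpoint is still listed, that fits an oversight just as well.
- **The day 0 start in Protocol 3.7 counts pre-dose events.** Day 0/1 is the screening and baseline record, which is needed to judge what is new. SAP 4.2 sets no such window.

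It is also fair to say that power for these comparisons is low on any denominator under the assumed rates, and that the protocol's background puts preventing ventilation first among treatment targets. Both points keep this below the level of a primary-endpoint problem.

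**Conclusion.** The point holds as two omissions in the SAP. Incidence of new oxygen use is a listed secondary endpoint with no analysis and no output row. This follows from the text and rests on no assumption. The duration analysis names no at-risk group and does not define new oxygen, although some participants are already on oxygen at entry.

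The size of the second omission is conditional. If those already on oxygen are scored zero, the variance of the log rate ratio rises by about 1.2 to 1.8 times, assuming 20-40% at risk and a squared coefficient of variation of 1 to 3, with the offset ignored. The rate ratio itself is not biased. As a separate matter, the ICU-time offset makes 9.2.7 unworkable for anyone never in ICU. The point should be fixed, in proportion to a secondary endpoint.

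**What to change.** 1. Define new oxygen use in SAP 4.3: categories 4 to 6 on the ordinal scale after first dose, to day 29, in participants at category 3 before dosing.
2. Add its incidence to SAP 9.2 and Table 9 as n (%) by arm, with a risk ratio and 95% CI. Use Fisher's exact test as in 9.2.8, or a model adjusted for age. Adjusting for site as well would be fragile: 80 to 160 people across 15 Trusts/Boards average 80/15 = 5.3 to 160/15 = 10.7 each.
3. Report deaths without prior oxygen separately, or as a sensitivity composite. Neither document lists a composite with death, so it should not replace the endpoint.
4. Restrict 9.2.7 to the same participants and remove the time-in-ICU offset there.
5. Make the change before results by arm are seen.

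The restriction uses a pre-dose characteristic, so the comparison remains randomised. The cost is a few SAP sentences and one table row. The ordinal scale is already recorded daily in hospital and at scheduled contacts. There are two downsides: fewer participants in 9.2.7, and no capture of oxygen used after discharge, because categories 1 and 2 do not identify it and the oxygen record stops at discharge. State the second as a limitation.
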